7. CRITERIA FOR STUDY DISCONTINUATION GENERAL

CRITERIA

- Inability of patient to comply with study requirements
- Determination by the investigator that it is no longer safe for the patient to continue therapy
- Disease progression
- Patient's preference

The responsible local clinical Investigator as well as MDACC IND Office, Celgene and Genentech have the right to discontinue this study at any time for reasonable medical or administrative reasons in any single center. Possible reasons for termination of the study could be but are not limited to:

- Unsatisfactory enrollment with respect to quantity or quality
- Inaccurate or incomplete data collection
- Falsification of records
- Failure to adhere to the study protocol.

8. CLINICAL AND LABORATORY EVALUATIONS

PRETREATMENT EVALUATIONS

Pretreatment evaluation will include:

- Medical history and a physical examination including vital signs ECOG performance status, height and weight and recording of concurrent medications (within 7 days of day 1).
- Hematology: complete CBC and differential, peripheral blood lymphocyte subsets (CD4, CD8, NK) and immunoglobulin levels (within 7 days of registration).
- Serum chemistry. This will include sodium, potassium, calcium, BUN, creatinine, glucose, albumin, total protein, alkaline phosphatase, LDH, total bilirubin, ALT(SGPT), uric acid, and TSH. Beta-2-microglobulin (within 7 days of day 1).
- Serology for HBV, HIV and HCV (within 3 months of registration).

Bone marrow aspiration and biopsy within one month from registration. Bone marrow will be evaluated for flow cytometry, for clonality and for IgVH mutational status (unless known), ZAP-70 (unless known) and CD38 expression, cytogenetic and genomic abnormalities by FISH (unless known).

- CT SCAN or/and PET and/or US and/or MRI within 30 days of registration if clinically indicated.

- For FCBP (female of childbearing potential) serum and/or urine pregnancy test must be done within 10 -14 days prior to start therapy and 24 hours prior to prescribe lenalidomide for cycle 1. Females of childbearing potential (FCBP) is a sexually mature female who:1) has not undergone a hysterectomy or bilateral oophorectomy; 2) has not been naturally postmenopausal for at least 24 consecutive months (i.e., has not had menses at any time in the preceding 24 consecutive months).

EVALUATIONS DURING TREATMENT

- Clinic visits (this will include vital signs and physical exam) at the University of Texas , MD Anderson Cancer Center (UTMDACC) are required for treatment initiation and at the start of cycles 2-6 (+/10 days from Day 1). Clinic visits (this will include vital signs and physical exam) at UTMDACC are required after 3, 6 cycles (obinutuzumab and lenalidomide) and 12 cycles (lenalidomide) and once every 6 cycles thereafter (+/-14 days from Day 1 of subsequent cycle). Hematology complete blood counts (white blood cells, hemoglobin, platelets and differential) will be monitored once weekly for the first five weeks and once every two weeks in case of dose increase until a stable dose of lenalidomide has been established for the specific patient (the once every two weeks laboratory monitoring will not apply if the dose is decreasing for non-hematological or laboratory measurable toxicity), and every two or four weeks thereafter.
- Serum chemistry basic metabolic profile (sodium, potassium, BUN, creatinine and glucose) will be monitored once a week for the first five weeks and then once every two weeks until a stable dose of lenalidomide has been established for the specific patient and then every two or four weeks thereafter.
- TSH, beta-2-microglobulin ,lymphocyte subsets, immunoglobulin levels , bone marrow biopsy and aspiration, flow cytometry will be performed and evaluated after 3, 6 cycles (obinutuzumab and lenalidomide) and after 12 cycles (lenalidomide).
- If patient stay on the study past 12 cycles, once every 6 cycles, he will have a bone marrow biopsy and aspirate evaluated by flow cytometry to check the status of the disease if clinically indicated.
- Blood lymphocyte subsets (CD4, CD8, NK) and immunoglobulin levels every 3 months for the first year, and once every 6 months thereafter.
- CT scan and/or PET, and/or US and/or MRI as clinical indicated
- Response to treatment will be assessed according to IW-CLL 2008 criteria.

- FCBP with regular or no menstruation must have a pregnancy test weekly for the first 28 days and then every 28 days while on therapy (including breaks in therapy); at discontinuation of lenalidomide and at day 28 post the last dose of lenalidomide. Females with irregular menstruation must have a pregnancy test weekly for the first 28 days and then every 14 days while on therapy (including breaks in therapy), at discontinuation of lenalidomide and at day 14 and day 28 post the last dose of lenalidomide (see Appendix 4 Risks of Fetal Exposure, Pregnancy Testing Guidelines and Acceptable Birth Control Methods).
- In the event of medically significant unexplained abnormal laboratory test values, the tests should be repeated and followed until they have returned to the normal range, baseline value and/or an adequate explanation of the abnormality is found. If a clear explanation is established it should be recorded on the eCRF.

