Hematology complete blood counts (white blood cells, hemoglobin, platelets and differential) will be monitored once weekly for the first five weeks and once every two weeks in case of dose increase until a stable dose of lenalidomide has been established for the specific patient (the once every two weeks laboratory monitoring will not apply if the dose is decreasing for non-hematological or laboratory measurable toxicity), and then every four weeks thereafter. Serum chemistry basic metabolic profile (sodium, potassium, BUN, creatinine and glucose) will be monitored once a week for the first five weeks and then once every two weeks until a stable dose of lenalidomide has been established for the specific patient and then every four weeks thereafter .

Additionally , beta-2-microglobulin , lymphocyte subsets, immunoglobulin levels will be performed and evaluated by flow cytometry after 3,6 cycles (obinutuzumab and lenalidomide) and after 12 cycles (lenalidomide).

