Venous thrombosis/embolism grade 3	
 Hold (interrupt) dose and start anticoagulant; restart at investigator's discretion (maintain dose level)
Hepatic or other non-hematologicic toxicity assessed as lenalidomide-related c >/= grade 3	
 Hold (interrupt) the dose and follow at least weekly until resolution and stabilization If the toxicity resolves to </= grade 2, implement the dose reduction step
Tumor flair refractory to oral pain medications	
 Hold (interrupt) dose and differentiate tumor flare from progression. Restart therapy at the investigator's discretion

a In patients with cytopenia at baseline, dose modifications will be based on the NCI grading scale for

haematological toxicity in CLL/SLL studies (see Table 2).

b Once toxicity has resolved, lenalidomide dose can be increased to 10 mg/daily at the discretion of the investigator or the dose that is clinically indicated.

c Further dose reduction will be allowed at the discretion of the investigator in case of persistent non haematological toxicity of grade 3 or less and in case of a change in laboratory evaluation such as platelet count, ANC, or hemoglobin count that indicates upcoming myelosuppression or as clinically indicated.

d For patients who experienced TFRs while treated with lenalidomide-containing

regimens, steroids will be allowed to manage lymph node enlargement and inflammation, and antihistamines to manage rash/pruritus. For patients with bulky(> 5 cm) lymph-nodes before the start of therapy, tumor flair prophylaxis with steroids may be considered for the first 10-14 days of therapy.

Table 6 Dose level for lenalidomide.

Level	10 mg Dose	5 mg Dose
-1	5 mg daily	5 mg daily, day 1-21 of a 28 days cycle or 5 mg every other day for 28 days
-2	5 mg daily, day 1-21 of a 28 days cycle or 5 mg every other day for 28 days	5 mg twice a week
-3	5 mg twice a week	5 mg once a week
-4	5 mg once a week	N/A

CONCOMITANT MEDICATIONS

Concomitant therapy

All concomitant medications should be recorded in the patient electronic records.

Prophylaxis for Tumor Lysis Syndrome

All patients should then be carefully monitored during the initial weeks of treatment. Patients still considered at risk for TLS because of persistently high tumor burden before the second and subsequent infusions of obinutuzumab should continue TLS prophylaxis until the risk is abated, as determined by the investigator.

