The investigator should expeditiously report any SAE occurring after a patient has completed or discontinued study participation if attributed to prior obinutuzumab exposure. If the investigator should become aware of the development of cancer or a congenital anomaly in a subsequently conceived offspring of a female patient who participated in the study, this should be reported as an SAE.

Safety Reconciliation

The Sponsor agrees to conduct reconciliation for the product. Genentech and the Sponsor will agree to the reconciliation periodicity and format, but agree at minimum to exchange monthly line listings of cases received by the other party. If discrepancies are identified, the Sponsor and Genentech will cooperate in resolving the discrepancies. The responsible individuals for each party shall handle the matter on a case-by-case basis until satisfactory resolution.

Adverse Events of Special Interest (AESIs)

AEs of special interest (AESIs) are defined as a potential safety problem, identified as a result of safety monitoring of the Product.

The following AEs are considered of special interest and must be reported to the Sponsor expeditiously irrespective of regulatory seriousness criteria:

- TLS (Tumor Lysis Syndrome; all grades)
- Abnormal Liver Functions Tests

Cases of potential drug-induced liver injury that include an elevated ALT or AST in combination with either an elevated bilirubin or clinical jaundice, as defined by Hy's law.

The finding of an elevated ALT or AST ($> 3 \times \text{ULN}$) in combination with either an elevated total bilirubin ($> 2 \times \text{ULN}$) or clinical jaundice in the absence of cholestasis or other causes of hyperbilirubinemia is considered to be an indicator of severe liver injury. Therefore, investigators must report as an adverse event the occurrence of either of the following:

- Treatment-emergent ALT or AST $> 3 \times \text{ULN}$ in combination with total bilirubin $> 2 \times \text{ULN}$

- Treatment-emergent ALT or AST $> 3 \times$ ULN in combination with clinical jaundice
- Suspected transmission of an infectious agent by the study drug, as defined below:

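### The written on-treatment chemistry panel contains no ALT, AST or bilirubin and covers tumor lysis only through potassium and creatinine, so hepatic and some metabolic toxicity would be under-counted

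*Combined protocol and SAP*

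**What the plan says.** **Scheduled on treatment.** Section 8 (Evaluations During Treatment) reads "Serum chemistry basic metabolic profile (sodium, potassium, BUN, creatinine and glucose) will be monitored once a week for the first five weeks", then continues at longer intervals. Section 3 (Safety Outcome Measures) names the same five analytes. The other scheduled laboratory work is the blood count and, at response assessments, "TSH, beta-2-microglobulin ,lymphocyte subsets, immunoglobulin levels , bone marrow biopsy and aspiration, flow cytometry will be performed and evaluated after 3, 6 cycles" and again after 12 cycles. Pregnancy tests apply to some patients, and HBV DNA follow-up to others.

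**Scheduled before treatment.** The Section 8 pretreatment list is longer. It includes calcium, alkaline phosphatase and LDH and ends with "total bilirubin, ALT(SGPT), uric acid, and TSH". AST and phosphate are not on it.

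**What the rules act on.**
- Section 10 makes two AESIs reportable on an expedited basis: "Cases of potential drug-induced liver injury that include an elevated ALT or AST in combination with either an elevated bilirubin or clinical jaundice", and "TLS (Tumor Lysis Syndrome; all grades"). The liver thresholds are ALT or AST above 3 x ULN with either total bilirubin above 2 x ULN or clinical jaundice.
- Table 5 in Section 6 ties a lenalidomide action to "Hepatic or other non-hematologicic toxicity assessed as lenalidomide-related" at grade 3 or higher.
- Section 6 (Tumor Lysis Syndrome) ties an obinutuzumab action to evidence of TLS, without a laboratory definition.
- Section 10 (Method of Analysis) stops the trial on the rate of grade 3 or higher non-hematological toxicity, with the boundaries in Table 8.

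**The concern.** A safety rule can only count what is measured. The pretreatment list shows that the authors write out a full chemistry panel when they intend one, so the five named on-treatment analytes are hard to read as shorthand for it. Followed as written, the schedule leaves a raised transaminase or bilirubin in a patient without symptoms to be found by some other test, at a time the plan does not set.

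Two things are at stake. Safety of the combination is a secondary endpoint, and its hepatic component would depend on who happened to be tested. The stopping rule counts patients with grade 3 or higher non-hematological toxicity, so a patient whose only qualifying event is an undetected laboratory abnormality is counted as free of toxicity. The error runs one way, towards continuing the trial.

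The plan's background makes tumor lysis relevant. It reports severe tumor lysis in an earlier single-agent lenalidomide study and one grade 3 tumor lysis with lenalidomide plus rituximab.

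**Working it through.** **Step 1. Inputs needed against inputs scheduled.**

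| Rule | Laboratory input | In the on-treatment panel of Sections 3 and 8? |
|---|---|---|
| Liver AESI, first criterion | ALT or AST, and total bilirubin | None of the three |
| Liver AESI, second criterion | ALT or AST, with clinical jaundice | Neither ALT nor AST |
| Table 5, hepatic toxicity grade 3 or higher (laboratory-detected) | Liver tests | None |
| TLS, all grades | Not defined in the text | Potassium and creatinine yes; uric acid, calcium and phosphate no |

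The liver AESI has 0 of 3 laboratory inputs scheduled. TLS coverage is partial.

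**Step 2. Reproduce the plan's stopping probability.** Table 8 stops at 8 or more of 10, or 14 or more of 20. The boundary at 30 coincides with full enrollment and is not an early stop. With X the number of toxicities in the first 10 patients, Y the number in the next 10, and true rate p:

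P(stop by 20) = P(X >= 8) + sum over x = 0 to 7 of P(X = x) * P(Y >= 14 - x), with X and Y both Binomial(10, p).

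At p = 0.70 this is 0.383 + 0.266 = 0.649. Table 9 combines futility and toxicity. At a response rate of 0.5, the Table 7 boundaries (1 of 10, 4 of 20) give a futility stop of 0.015 by the same recursion. If response and toxicity are independent, 1 - (1 - 0.015)(1 - 0.649) = 0.654, which matches the 0.65 in Table 9.

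**Step 3. Effect of missed events.** Let s be the share of all patients whose only grade 3 or higher non-hematological toxicity is a laboratory event that is not detected. The rule then sees p - s instead of p. The documents give no value for s, so a range is shown.

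| True rate p | s = 0 | s = 1% | s = 2% | s = 5% |
|---|---|---|---|---|
| 0.70 | 0.649 | 0.613 | 0.577 | 0.468 |
| 0.60 | 0.301 | 0.272 | 0.245 | 0.173 |
| 0.50 | 0.089 | 0.077 | 0.066 | 0.041 |

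Each entry is the Step 2 formula evaluated at p - s.

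**Step 4. What the documents offer on s.** The nearest figure is the single grade 3 tumor lysis with lenalidomide plus rituximab. That study reports 14 patients as 24%, so about 14 / 0.24 = 58 patients, and 1 / 58 = 1.7%. The event is not said to have been laboratory-only. The amended single-agent lenalidomide study reports no further tumor lysis among 25 patients. No corresponding liver figure is given.

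**The case against.** The strongest reply is that the written panel is not the whole of the plan. The Study Calendar (Appendix 2) and the two package inserts (Appendices D and E) are not in the text reviewed, and Section 3 also refers to routine blood tests without naming them. Any of these may carry liver or TLS monitoring. This stands: a reader might infer that the trial has no on-treatment liver testing at all, and the documents do not support that. It does not remove the need to reconcile. If the calendar lists these tests, it disagrees with two sections that name the panel analyte by analyte.

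There are also other routes to detection. Examination visits are scheduled, Section 6 asks for careful monitoring in the initial weeks under its TLS heading, and Section 10 accepts adverse events found by any means. This also stands. The defect is unsystematic ascertainment; detection is not impossible.

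Two further readings are tempting and fail:
- That TLS reporting cannot be triggered from scheduled data. Potassium and creatinine are measured weekly for the first five weeks, and the text has no laboratory definition of TLS against which to call the panel insufficient.
- That the liver AESI falls back on visible jaundice. Both criteria require ALT or AST, so jaundice alone never meets it.

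Finally, the drop from 0.65 to 0.47 needs both a 5% share and a 70% toxicity rate. Neither is an expected value taken from the documents.

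**Conclusion.** The point holds for the schedule written in Sections 3 and 8. That schedule supplies none of the laboratory inputs for the liver AESI or for laboratory-detected hepatic toxicity under Table 5, and only part of what might show TLS. The direction of the bias is certain for any event that goes undetected: the toxicity count and the safety endpoint are too low.

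The size is not known. At a true rate of 0.70, a missed share of 1% to 2% costs about 4 to 7 percentage points of the chance of stopping by 20 patients, and 5% costs about 18. At a true rate of 0.50 even 5% costs about 5 points. These figures assume independent patients and that no event in the missed share is found by another route, so unscheduled testing would make the loss smaller. This should be corrected because it is cheap and concerns safety data. It does not show that the stopping rule is unsound.

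**What to change.** Reconcile the on-treatment panel in Section 3 (Safety Outcome Measures) and Section 8 (Evaluations During Treatment), and the Study Calendar, with the TLS text and Table 5 in Section 6 and the AESI list in Section 10:

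- Include ALT, AST and total bilirubin in the chemistry samples already scheduled.
- State which analytes the sponsor uses to define laboratory TLS, and include those in the same samples.
- Add AST, and any TLS analyte not yet listed, to the pretreatment list, so that treatment-emergent change can be judged against a baseline.
- If the Study Calendar already lists these tests, correct Sections 3 and 8 to match it.

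Draw times and visits do not change. The cost is a small laboratory charge and more low-grade laboratory adverse events to record.

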9. EVALUATION OF RESPONSE

The primary efficacy endpoint is overall response, defined as CR or PR. The secondary endpoints will be safety of the combination, response according to prognostic markers at diagnosis, time to next treatment and overall survival. Response to treatment will be assessed according to NCI-WG 2008 working group criteria at 3 months from the beginning of therapy and every 6 months thereafter.

10. STATISTICAL CONSIDERATIONS

DETERMINATION OF SAMPLE SIZE

The patient sample size will be 30 patients and the Bayesian method of Thall, Simon and Estey²¹ will be employed to perform interim futility and safety monitoring.

PLANNED EFFICACY EVALUATIONS

The primary efficacy endpoint is overall response, defined as CR or PR. The secondary endpoints will be safety of the combination, response according to prognostic markers at diagnosis, time to next treatment and overall survival. Response to treatment will be assessed according to NCI-WG 2008 working group criteria at 3, 6 months from the beginning of therapy and every 6 months thereafter.

PRIMARY EFFICACY VARIABLES

Overall response, defined as CR or PR.

SECONDARY EFFICACY VARIABLES

The secondary endpoints will be safety of the combination, response according to prognostic markers at diagnosis, time to next treatment and overall survival.

METHOD OF ANALYSIS

We will monitor futility and safety of the treatment combination using a Bayesian design by Thall, Simon and Estey, in cohort size of 10. Specifically, assuming a beta (0.8, 1.2) prior for the overall response (OR) rate, we will stop trial if $\text{Prob}\{p(\text{OR}) > 0.40 \text{ data}\} < 0.05$, where $p(\text{OR})$ is the probability of overall response. That is, if at any time during the trial we determine that there is less than 5% chance that the overall response rate is at least 40%, we will stop the trial. For futility monitoring purpose, we will assess patients' OR rate at 3 months post treatment, and at each planned cohort (i.e., 10, 20, 30, etc.) for interim look, if there is not enough number of responders (such as 1 or fewer out of the first 10, 4 or fewer out of the first 20, etc.) we will temporarily suspend accrual until all patients in the current cohort has been fully evaluated. Similarly, we will stop the trial if $\text{Prob}\{p(\text{TOX}) > 0.50 \text{ data}\} > 0.95$, where $p(\text{TOX})$ is the probability of grade 3 or higher non-hematological toxicity and a beta(1, 1) prior was used for toxicity rate. That is, if at any time during the trial we determine that there is more than 95% chance that the toxicity rate is at least 50%, we will stop the trial due to safety concern. The corresponding stopping boundaries for futility and safety are shown in Tables 7 and 8 respectively. The operating characteristics of the design are illustrated in Table 9. Multc Lean Desktop (v2.1.0) was used for generating the stopping boundaries and the OC table.

If the trial did not stop due to either futility or toxicity, then with a total sample size of 30, the 95% credible interval for the overall response rate will be (0.24, 0.57), assuming an OR rate of 0.40 and a beta(0.8, 1.2) prior.

The proportion of patients achieving OR and its 95% credible interval will be presented. In addition, we will compute the posterior probability of OR rate being greater than 40%. Similar methods will be used to analyze the toxicity data. Univariate and multivariable logistic regression models will be fit to assess the association between OR and prognostic biomarkers. The time-to-event outcomes (such as time to next treatment or overall survival) will be estimated using the Kaplan-Meier method.

Table 7. Interim futility stopping boundaries in cohort size of 10.

Number of Patients Evaluated	Stop the trial if \leq OR Observed
10	1
20	4
30	7

Table 8. Interim toxicity stopping boundaries in cohort size of 10.

Among These Number of Patients	Stop the trial if >/= Toxicity Observed
10	8
20	14
30	20
-	-

Table 9 The operating characteristics of futility and toxicity monitoring.

True OR rate	True Toxicity Rate	Prob (stop early)	Average number of patients
0.3	0.3	0.28	25.6
0.3	0.5	0.35	24.5
0.3	0.7	0.75	17.8
0.4	0.3	0.08	28.7
0.4	0.5	0.16	27.4
0.4	0.7	0.68	19.1
0.5	0.3	0.02	29.7
0.5	0.5	0.10	28.3
0.5	0.7	0.65	19.6

In addition, we will monitor the grade 4 and grade 5 non-hematological toxicities separately, throughout the study and in cohort size of 10. Specifically, the trial will be stopped if $\text{Prob}\{p(\text{TOX4}) > 0.25 | \text{data}\} > 0.95$ or $\text{Prob}\{p(\text{TOX5}) > 0.10 | \text{data}\} > 0.95$, where $p(\text{TOX4})$ and $p(\text{TOX5})$ are the probabilities of grade 4 and grade 5 non-hematological toxicities, respectively. A beta(0.5, 1.5) prior is assumed for $p(\text{TOX4})$ and a beta(0.2, 1.8) prior is assumed $p(\text{TOX5})$. Based on these stopping criteria, the trial will be stopped early if $[\#\text{patients with grade 4 toxicities}] / [\#\text{patients evaluated}] \geq 6/10, 9/20, 12/30$ OR $[\#\text{patients with grade 5 toxicities}] / [\#\text{patients evaluated}] \geq 4/10, 5/20, 7/30$.

This protocol will use PDMS and CORE as database repositories

REPORTING OF ADVERSE EVENTS ASSESSMENT OF SAFETY

Safety assessments will consist of monitoring and reporting AEs and SAEs that are considered related to obinutuzumab or/and lenalidomide, all events of death, and any study specific issue of concern.

Adverse Events

An AE is any unfavorable and unintended sign, temporarily associated with the use of an

investigational medicinal product (IMP) or other protocol- imposed intervention , regardless of attribution.

Serious Adverse Event Reporting for MD Anderson- Sponsored IND Protocols

An adverse event or suspected adverse reaction is considered “serious” if, in the view of either the investigator or the sponsor, it results in any of the following outcomes:

Death

A life-threatening adverse drug experience – any adverse experience that places the patient, in the view of the initial reporter, at immediate risk of death from the adverse experience as it occurred. It does not include an adverse experience that, had it occurred in a more severe form, might have caused death.

Inpatient hospitalization or prolongation of existing hospitalization

A persistent or significant incapacity or substantial disruption of the ability to conduct normal life functions.

A congenital anomaly/birth defect.

Important medical events that may not result in death, be life-threatening, or require hospitalization may be considered a serious adverse drug experience when, based upon appropriate medical judgment, they may jeopardize the patient or subject and may require medical or surgical intervention to prevent one of the outcomes listed in this definition. Examples of such medical events include allergic bronchospasm requiring intensive treatment in an emergency room or at home, blood dyscrasias or convulsions that do not result in inpatient hospitalization, or the development of drug dependency or drug abuse (21 CFR 312.32).

Important medical events as defined above, may also be considered serious adverse events. Any important medical event can and should be reported as an SAE if deemed appropriate by the Principal Investigator or the INDIND Sponsor, IND Office.

All events occurring during the conduct of a protocol and meeting the definition of a SAE must be reported to the IRB in accordance with the timeframes and procedures outlined in “The University of Texas M. D. Anderson Cancer Center Institutional Review Board Policy for Investigators on Reporting Unanticipated Adverse Events for Drugs and Devices”. Unless stated otherwise in the protocol, all SAEs, expected or unexpected, must be reported to the IND Office, regardless of attribution (within 5 working days of knowledge of the event).

Unless otherwise noted, the electronic SAE application (eSAE) will be utilized for safety reporting to the IND Office and MDACC IRB for participants enrolled at MDACC.

Reporting for all sites:

- **All life-threatening or fatal events**, that are unexpected, and related to the study drug, must have a written report submitted within **24 hours** (next working day) of knowledge of the event to the Safety Project Manager in the IND Office. -
- **Serious adverse events will be captured from the time of the first protocol-specific intervention, until 30 days after the last dose of drug, unless the participant withdraws consent. Serious adverse events must be followed until clinical recovery is complete and laboratory tests have returned to baseline, progression of the event has stabilized, or there has been acceptable resolution of the event.**
- **Additionally, any serious adverse events that occur after the 30 day time period that are related to the study treatment must be reported to the IND Office. This may include the development of a secondary malignancy.**
- **All events reported to the supporting company must also be report to the IND Office.**

Reporting to FDA:

- Serious adverse events will be forwarded to FDA by the IND Sponsor (Safety Project Manager IND Office) according to 21 CFR 312.32.

It is the responsibility of the PI and the research team to ensure serious adverse events are reported according to the Code of Federal Regulations, Good Clinical Practices, the protocol

guidelines, the sponsor's guidelines, and Institutional Review Board policy.

Genetech requested reporting:

Adverse Events

An AE is any unfavorable and unintended sign, symptom, or disease temporally associated with the use of an investigational medicinal product (IMP) or other protocol-imposed intervention, regardless of attribution.

This includes the following:

AEs not previously observed in the patient that emerge during the protocol-specified AE reporting period, including signs or symptoms associated with CLL/SLL that were not present prior to the AE reporting period.

Complications that occur as a result of protocol-mandated interventions (e.g., invasive procedures such as cardiac catheterizations).

If applicable, AEs that occur prior to assignment of study treatment associated with medication washout, no treatment run-in, or other protocol-mandated intervention.

Preexisting medical conditions (other than the condition being studied) judged by the investigator to have worsened in severity or frequency or changed in character during the protocol-specified AE reporting period.

Serious Adverse Events

An AE should be classified as an SAE if the following criteria are met:

It results in death (i.e., the AE actually causes or leads to death).

It is life threatening (i.e., the AE, in the view of the investigator, places the patient at immediate risk of death. It does not include an AE that, had it occurred in a more severe form, might have caused death.).

It requires or prolongs inpatient hospitalization.

It results in persistent or significant disability/incapacity (i.e., the AE results in substantial disruption of the patient's ability to conduct normal life functions).

It results in a congenital anomaly/birth defect in a neonate/infant born to a mother exposed to the IMP. It is considered a significant medical event by the investigator based on medical judgment (e.g., may jeopardize the patient or may require medical/surgical intervention to prevent one of the outcomes listed above).

METHODS AND TIMING FOR ASSESSING AND RECORDING SAFETY VARIABLES

The investigator is responsible for ensuring that all AEs and SAEs, that are observed or reported during the study, are collected and reported to the U.S. Food and Drug Administration (FDA), appropriate IRB(s), and Genentech, Inc. in accordance with CFR 312.32 (IND Safety Reports).

Adverse Event Reporting Period

The study period during which all AEs and SAEs must be reported begins after informed consent is obtained and initiation of study treatment and ends 30 days following the last administration of study treatment or study discontinuation/termination, whichever is earlier. After this period, investigators should only report SAEs that are attributed to prior study treatment.

Assessment of Adverse Events

All AEs and SAEs whether volunteered by the patient, discovered by study personnel during questioning, or detected through physical examination, laboratory test, or other means will be reported appropriately. Each reported AE or SAE will be described by its duration (i.e., start and end dates), regulatory seriousness criteria if applicable, suspected relationship to the obinutuzumab (see following guidance), and actions taken.

To ensure consistency of AE and SAE causality assessments, investigators should apply the following general guideline:

Yes

There is a plausible temporal relationship between the onset of the AE and administration of the obinutuzumab and the AE cannot be readily explained by the patient's clinical state, intercurrent illness, or concomitant therapies; and/or the AE follows a known pattern of response to the obinutuzumab and/or the AE abates or resolves upon discontinuation of the obinutuzumab or dose reduction and, if applicable, reappears upon re-challenge.

No

Evidence exists that the AE has an etiology other than the obinutuzumab (e.g., preexisting medical condition, underlying disease, intercurrent illness, or concomitant medication); and/or the AE has no plausible temporal relationship to obinutuzumab administration (e.g., cancer diagnosed 2 days after first dose of obinutuzumab).

Expected AEs are those AEs that are listed or characterized in the Package Insert or current Investigator Brochure.

Unexpected AEs are those not listed in the Package Insert (P.I.) or current Investigator's Brochure or not identified. This includes AEs for which the specificity or severity is not consistent with the description in the P.I. or Investigator's Brochure. For example, under this definition, hepatic necrosis would be unexpected if the P.I. or Investigator's Brochure only referred to elevated hepatic enzymes or hepatitis.

PROCEDURES FOR ELICITING, RECORDING, AND REPORTING ADVERSE EVENTS

Eliciting Adverse Events

A consistent methodology for eliciting AEs at all patient evaluation timepoints should be adopted. Examples of non-directive questions include:

“How have you felt since your last clinical visit?”

“Have you had any new or changed health problems since you were last here?

Specific Instructions for Recording Adverse Events

Investigators should use correct medical terminology/concepts when reporting AEs or SAEs. Avoid colloquialisms and abbreviations.

Diagnosis versus Signs and Symptoms

If known at the time of reporting, a diagnosis should be reported rather than individual signs and symptoms (e.g., record only liver failure or hepatitis rather than jaundice, asterixis, and elevated transaminases). However, if a constellation of signs and/or symptoms cannot be medically characterized as a single diagnosis or syndrome at the time of reporting, it is acceptable to report the information that is currently available. If a diagnosis is subsequently established, it should be reported as follow-up information.

Deaths

All deaths that occur during the protocol-specified AE reporting period regardless of attribution, will be reported to the appropriate parties. When recording a death, the event or condition that caused or contributed to the fatal outcome should be reported as the single medical concept. If the cause of death is unknown and cannot be ascertained at the time of reporting, report “Unexplained Death”.

Preexisting Medical Conditions

A preexisting medical condition is one that is present at the start of the study. Such conditions should be reported as medical and surgical history. A preexisting medical condition should be re-assessed throughout the trial and reported as an AE or SAE only if the frequency, severity, or character of the condition worsens during the study. When reporting such events, it is important to convey the concept that the preexisting condition has changed by including applicable descriptors (e.g., “more frequent headaches”).

Hospitalizations for Medical or Surgical Procedures

Any AE that results in hospitalization or prolonged hospitalization should be documented and reported as an SAE. If a patient is hospitalized to undergo a medical or surgical procedure as a result of an AE, the event responsible for the procedure, not the procedure itself, should be reported as the SAE. For example, if a patient is hospitalized to undergo coronary bypass surgery, record the heart condition that necessitated the bypass as the SAE.

- Hospitalizations for the following reasons do not require reporting:
- Hospitalization or prolonged hospitalization for diagnostic or elective surgical procedures for preexisting conditions
- Hospitalization or prolonged hospitalization required to allow efficacy measurement for the study or
- Hospitalization or prolonged hospitalization for scheduled therapy of the target disease of the study.

Pregnancy

If a female patient becomes pregnant while receiving obinutuzumab or within one year after the last dose of obinutuzumab, or the partner of a male patient becomes pregnant while receiving therapy or within three months of completing therapy, a report should be completed and expeditiously submitted to the Genentech, Inc. Follow-up to obtain the outcome of the pregnancy should also occur. Abortion, whether accidental, therapeutic, or spontaneous, should always be classified as serious, and expeditiously reported as an SAE. Similarly, any congenital anomaly/birth defect in a child born to a female patient exposed to obinutuzumab should be reported as an SAE.

Post-Study Adverse Events

The investigator should expeditiously report any SAE occurring after a patient has completed or discontinued study participation if attributed to prior obinutuzumab exposure. If the investigator should become aware of the development of cancer or a congenital anomaly in a subsequently conceived offspring of a female patient who participated in the study, this should be reported as an SAE.

Safety Reconciliation

The Sponsor agrees to conduct reconciliation for the product. Genentech and the Sponsor will agree to the reconciliation periodicity and format, but agree at minimum to exchange monthly line listings of cases received by the other party. If discrepancies are identified, the Sponsor and Genentech will cooperate in resolving the discrepancies. The responsible individuals for each party shall handle the matter on a case-by-case basis until satisfactory resolution.

Adverse Events of Special Interest (AESIs)

AEs of special interest (AESIs) are defined as a potential safety problem, identified as a result of safety monitoring of the Product.

The following AEs are considered of special interest and must be reported to the Sponsor expeditiously irrespective of regulatory seriousness criteria:

- TLS (Tumor Lysis Syndrome; all grades)
- Abnormal Liver Functions Tests

Cases of potential drug-induced liver injury that include an elevated ALT or AST in combination with either an elevated bilirubin or clinical jaundice, as defined by Hy's law.

The finding of an elevated ALT or AST ($> 3 \times \text{ULN}$) in combination with either an elevated total bilirubin ($> 2 \times \text{ULN}$) or clinical jaundice in the absence of cholestasis or other causes of hyperbilirubinemia is considered to be an indicator of severe liver injury. Therefore, investigators must report as an adverse event the occurrence of either of the following:

- Treatment-emergent ALT or AST $> 3 \times \text{ULN}$ in combination with total bilirubin $> 2 \times \text{ULN}$

- Treatment-emergent ALT or AST $> 3 \times$ ULN in combination with clinical jaundice
- Suspected transmission of an infectious agent by the study drug, as defined below:
